#### **6.3.4 Laboratory Data**

Clinical laboratory tests on hematology, serum chemistry and electrolytes, serum lipids, urinalysis will be performed according to the schedule in Section 3.6. Investigators will assess whether there are any clinically significant abnormalities and record the abnormality on medical history or AE forms.

##### **Conversion to the International System of Units**

All laboratory data will be stored in the database with the units in which they are originally reported. Laboratory data in summary tables and subject data listings will be presented in the International System of Units (SI units; *Système International d'Unités*). Laboratory data not reported in SI units will be converted to SI units before further processing or data analysis.

##### **Abnormal Values**

Based upon laboratory normal ranges, laboratory test results will be categorized according to the normal range as low, normal and high. Subjects with laboratory data outside the normal range will be listed with abnormal values flagged.

**Table 4 Clinical Laboratory Tests**
**Hematology**

Hematocrit (Hct)	Mean corpuscular volume (MCV)
Hemoglobin (Hgb)	Platelet count
Mean corpuscular hemoglobin (MCH)	Red blood cell (RBC) count
Mean corpuscular hemoglobin concentration (MCHC)	White blood cell (WBC) count with differential

**Serum Chemistry and Electrolytes**

Albumin (ALB)	Calcium (Ca)
Alanine aminotransferase (ALT)	Magnesium
Aspartate aminotransferase (AST)	Phosphorus
Blood urea nitrogen (BUN)	Potassium (K)
Glucose	Sodium (Na)
Bicarbonate (HCO 3 )	Total bilirubin
Creatinine Chloride (Cl)	Direct bilirubin
Total protein	Uric acid

**Serum lipids**

Total cholesterol (TC)	Low-density lipoprotein cholesterol (LDL-C), calculated
High-density lipoprotein cholesterol (HDL-C)	
Triglycerides (TG)	

**Urinalysis**

Appearance	Nitrite
Bilirubin	Occult blood
Colour	pH
Glucose	Protein
Ketones	Specific gravity
Microscopic examination of sediment	Urobilinogen
	Leukocyte esterase

**Urine Collection**

Glucose	Potassium
Creatinine	Calcium
Sodium	Uric acid

**6.3.5 Vital Signs**

Vital signs include pulse (beats/min), SBP and DBP (mmHg), oral temperature (°C) and respiration rate (breaths/min).

Vital sign changes from baseline will be summarized by treatment.

Baseline values are those measured at last evaluation prior to administration of study drug in each treatment period.

Change from baseline to time point t, denoted  $\text{Change}_t$ , will be calculated as:

$$\text{Change}_t = \text{Value}_t - \text{Value}_{\text{Baseline}}$$

### **6.3.6 Electrocardiogram**

ECG parameters, including the RR interval (intra-beat interval), PR interval (the period that extends from the beginning of the P wave [the onset of atrial depolarization] until the beginning of the QRS complex [the onset of ventricular depolarization]), QRS duration, and QT interval (the corrected QT interval is the measure of the time between the start of the Q wave and the end of the T wave in the heart's electrical cycle), will be measured according to the study assessment schedule as specified in Section 3.6. Each ECG will be assessed by the Investigator for signs of ischemia, clinically significant hypertrophy, and clinically significant T-wave (repolarization of the ventricles) abnormalities. Baseline ECGs will be defined as the last evaluation performed prior to the administration of study drug in each treatment period.

ECG changes from baseline will be summarized by treatment.

Change from baseline to time point t, denoted  $\text{Change}_t$ , will be calculated as:

$$\text{Change}_t = \text{Value}_t - \text{Value}_{\text{Baseline}}$$

### **6.3.7 Physical Examination**

A complete PE will include measurement of body weight and height (height will be measured only at screening), general assessment of all body systems including the skin, head, eyes, ears, nose, throat, neck, lungs, heart, abdomen, lymph nodes, and extremities.

Physical examination results will be presented in individual subject data listings.

### **6.3.8 Pregnancy Test**

Only pregnancies considered by the investigator as related to study treatment (e.g., resulting from an interaction between study drug and a contraceptive medication) are considered AEs unto themselves. However, all pregnancies with an estimated conception date during the AE reporting period, must be recorded in the AE section of the eCRF. This applies to both pregnancies in female subjects and in female partners of male subjects.

### **6.3.9 Concomitant Medications/Treatments**

Concomitant medications administered at the time of randomization and during the study will be recorded on the case report form (CRF). The medication name, indication, dose, unit, frequency, route of administration, date(s) of administration and reason for administration will be recorded. This documentation should continue until discharge from the study.

A concomitant medication is any medication the subject enters the trial taking and is expected to continue taking for some portion of the trial, as well as any medication the subject takes during the course of the trial. All prescription and over-the-counter (OTC) medications (non-prescription drugs), including vitamins and herbal supplements, that subjects receive during the trial must be documented on the CRF. This documentation will continue until the subjects are discharged.

Concomitant medications will be coded using the World Health Organization Drug Dictionary (WHO-DD). A by-subject listing of concomitant medications will include all medications taken during the study.

All prior and concomitant medication will be presented in individual subject data listings.

For medications with incomplete dates, imputation will be used to convert to a complete date. Imputed dates will be used to determine Study Day.

Partial medication start dates will be imputed as follows:

1. Only the year is reported: If the subject started to receive study drug in the year reported, then the date of the first dose of study drug will be used as the starting date of the medication. Otherwise, January 1 will be used as the start of the medication.
2. The month and year is reported: If the subject started to receive study drug during the month and year reported, then the date of first dose of study drug will be used as the starting date of the medication. Otherwise, the first day of the month will be used as the start of the medication.

Partial medication end dates will be imputed for non-ongoing medications as follows:

1. Only the year is reported: If the subject stopped to receive study drug in the year reported, then the date of the last dose of study drug will be used as the end date of the medication. Otherwise, December 31 will be used as the end of the medication.
2. The month and year is reported: If the subject stopped to receive study drug during the month and year reported, then the date of last dose of study drug will be used as the end date of the medication. Otherwise, the last day of the month will be used as the end of the medication.

The above rules are subject to logical sense, for example, imputed start date should be on or prior to imputed end date.

Verbatim terms will be coded and assigned a preferred term and an ATC (anatomic therapeutic class) term.

## **7. PHARMACOKINETIC/PHARMACODYNAMIC ANALYSES**

### **7.1 General Considerations**

The PK Population will be used for PK analyses. The PD Population will be used for PD analyses.

Statistical and PK analyses will be performed by Everest Clinical Research. Statistical analysis will be performed using Statistical Analysis Software SAS for Windows® (SAS Institute Inc., USA). Non-compartmental analysis (NCA) will be performed using Phoenix® WinNonlin® 6.4 (Certara, USA).

### **7.2 Pharmacokinetic Analyses**

From the plasma bexagliflozin concentration-time data, the following PK parameters will be estimated for each subject where feasible.

**Table 3. Pharmacokinetic Parameters**

Pharmacokinetic Parameters	
$C_{\max}$	Maximum observed plasma concentration
$T_{\max}$	Time of maximum observed plasma concentration
$\lambda_z$	Terminal elimination phase rate constant
$T_{1/2}$	Apparent terminal elimination half life
CL/F	Apparent oral clearance
$V_z/F$	Apparent volume of distribution
$AUC_{0-t}$	Area under the plasma concentration-time curve from time 0 to time t (time of last quantifiable plasma concentration)
$AUC_{0-\infty}$	Area under the plasma concentration-time curve from time 0 to infinity

$C_{\max}$  and  $T_{\max}$  will be obtained directly from experimental observations. If multiple maxima occur at equal concentrations, the first temporal value will be taken.

The apparent terminal elimination half-life,  $T_{1/2}$ , where determinable, will be calculated as the natural log of 2 divided by the terminal phase rate constant,  $\lambda_z$ . The number of data points included in the regression will be determined by visual inspection, but a minimum of three data points in the terminal phase, excluding  $C_{\max}$ , is required to estimate  $\lambda_z$ . In order for the selection to take place the adjusted  $r^2$  value reported in Phoenix® WinNonlin® must be  $\geq 0.7$ .

$AUC_{0-t}$  and  $AUC_{0-\infty}$  will be calculated using the linear trapezoidal linear interpolation method, using actual elapsed time values. If the actual collection time is unknown the nominal collection time may be used for the purposes of PK parameter estimation. For the purpose of calculating AUC, all missing values will be treated as missing in the PK analysis and excluded from analysis except when they occur at pre-dose where they will be set to zero. All values that were below the limit of quantitation (BLOQ) prior to  $T_{\max}$  will be set to zero. BLOQ values that occur after  $T_{\max}$  will be set to missing. When  $\geq 2$  consecutive plasma concentrations below the limit of quantitation (BLOQ) are encountered after  $T_{\max}$ , these and all subsequent values will be excluded from the analysis.

$AUC_{0-\infty}$  will be calculated as outlined below:

$AUC_{0-\infty} = AUC_{\text{last}} + (C_{\text{last}} / \lambda_z)$ , where  $C_{\text{last}}$  is the last temporal quantifiable plasma concentration corresponding to  $T_{\text{last}}$ .

The proportion of  $AUC_{0-\infty}$  due to extrapolation ( $AUC_{\text{extr}}$ ) will be calculated and expressed as a percentage.  $AUC_{0-\infty}$  values will be considered unreliable estimates if the  $AUC_{\text{extr}}$  is greater than 20%.

CL/F will be calculated as  $\text{Dose} / AUC_{0-\infty}$ .

$V_z/F$  will be calculated as  $\text{Dose} / (\lambda_z \times AUC_{0-\infty})$ .

$T_{1/2}$  will be calculated as  $0.693 / \lambda_z$ .

Descriptive statistics for the plasma concentrations of bexagliflozin by Treatment and Timepoint will be provided. A listing of plasma concentrations by Subject Number, Treatment Period and Timepoint will also be provided.

To assess the lack of interaction effect of a high-fat meal on the PK of bexagliflozin, an analyses of variance (ANOVA) using a linear mixed-effects model will be fitted to the natural logarithmic transformation of PK parameters of bexagliflozin ( $C_{max}$ ,  $AUC_{0-t}$  and  $AUC_{0-\infty}$ ). The linear mixed-effects model will include subject as a random effect, and treatment, period, and sequence as fixed effects. The 90% confidence intervals (CIs) will be constructed for the fed: fasted ratio of the least squares (LS) geometric means of PK parameters ( $C_{max}$ ,  $AUC_{0-t}$  and  $AUC_{0-\infty}$ ), with 80-125% defined as the lack of interaction boundaries.

The ratios of geometric least squares means and corresponding 90% CI for the treatment comparison will be determined by exponentiating the mean differences between treatments on the logarithm scale. The intra-subject geometric CV%,  $100\% * \sqrt{\exp(\text{residual}) - 1}$ , where residual = the residual variance component and where exp is the natural exponential function, will be reported.

The appropriateness of the mixed model will be assessed through residual analyses. Any modifications required due to poor fit will be reported and executed.

Descriptive statistics for the PK parameters  $C_{max}$ ,  $T_{max}$ ,  $AUC_{0-\infty}$ ,  $AUC_{0-t}$ ,  $CL/F$ ,  $V_z/F$ ,  $\lambda_z$ , and  $T_{1/2}$  will be tabulated by treatment. Means, standard deviations (SD), medians, ranges (minimum; maximum), and geometric means and coefficients of variation (CV) will be presented for all PK parameters with the exception of  $T_{max}$ . Medians and ranges will be presented for  $T_{max}$ .

A listing of derived PK parameters of bexagliflozin by Subject Number and Treatment Period will be provided.

Refer to Appendix 2 for the SAS code.

### 7.3 Pharmacodynamic Analyses

Descriptive statistics of glucose concentrations and UGE will be summarized by Treatment and Timepoint.

The quantity of glucose excreted in urine will be determined by multiplying the urine glucose concentration for each time interval by the volume of urine collected for the corresponding collection interval. The total 24-hour and 48-hour quantity of glucose excreted in urine will be calculated by adding the amounts collected during each interval.

PD data will also be reported in listings.

The effect of a high-fat meal will be evaluated by comparing the mean cumulative UGE between subjects under fasted and fed (high-fat, high-calorie conditions). Potential effects on urinary creatinine, uric acid, sodium, potassium, and calcium will also be analyzed.

## 8. STATISTICAL ANALYSIS

### 8.1 General Data Handling Rules and Definitions

All data collected on case report forms will be provided in listings, except data collected only for confirmation of study entry criteria and for study administrative purposes. If any randomized patient is found to be without valid documented informed consent, that subject's data will be excluded from the report, except as necessary to document the error.

All statistical analyses will be conducted using SAS version 9.3 or newer.

Except where specified, all continuous variables will be summarized with descriptive statistics (the number of non-missing values, mean, standard deviation, median, minimum and maximum) and all categorical

variables will be summarized with frequency counts and percentages, by treatment. Unless otherwise specified, the mean and median will be displayed to 1 more decimal place than the original data, and standard deviation will be displayed to two more decimal places than the original data. All frequencies will be rounded to 1 decimal place.

Missing data will be maintained as missing unless specified otherwise. For variables where missing data is imputed, the analysis dataset will contain one variable with the imputed value and the original variable with missing maintained as missing.

## **8.2 Subject Disposition**

An overall disposition table for all subjects will be presented. This tabulation will include the number of subjects randomized, treated, not treated, completed, and those who discontinued early from the study along with the corresponding primary reasons for early termination. The number and percentage of randomized subjects who are included in the PK, Safety and PD Populations will also be tabulated.

Subject disposition by treatment and treatment sequence will also be summarized.

Subjects in the Safety Population who prematurely discontinued from the study will be summarized by primary reason for early termination.

All subjects in the Safety Population will be listed.

## **8.3 Demographic and Baseline Characteristics**

Demographic and baseline characteristics will be summarized by treatment and treatment sequence and listed.

Descriptive statistics (n, mean, median, standard deviation, minimum, and maximum) will be presented for continuous variables. Frequency distributions (counts and percentages) will be presented for categorical variables.

Medical and surgical history, physical examination, as well as prior and concomitant medications will be listed. Prior and concomitant medications will be listed with the drug names and ATC classification codes based on the data collected in the eCRF. The World Health Organization (WHO) Drug Dictionary, version March 2016 or newer, will be used to classify prior and concomitant medications by therapeutic class and drug name.

Abnormalities in the subjects' medical and surgical histories will be coded using version 19.0 (or newer) of MedDRA Medical Dictionary for Regulatory Activities, and summarized and listed.

## **8.4 Safety Analyses**

Safety analyses will be performed using the Safety Population, unless otherwise specified.

Safety measurements will include AEs, clinical laboratory tests (i.e. serum chemistry, hematology and urinalysis), ECGs, physical exams and vital signs. All safety data will be summarized by treatment. Baseline values for clinical laboratory tests, vital signs and ECGs will be defined as the last evaluation performed prior to administration of study drug.

### **8.4.1 Adverse Events**

All AEs will be coded to system organ class (SOC) and preferred term (PT) using the latest Medical Dictionary for Regulatory Activities coding dictionary (version to be specified in the clinical study report). All reported AEs will be listed, but only TEAEs will be summarized.

The incidence of all TEAEs will be summarized by treatment. In the summary tables, subjects may be counted under multiple SOCs and PTs, but for each SOC and PT, subjects are only counted once. If a subject has the same AE on multiple occasions, the highest severity (severe > moderate > mild) or drug relationship (definite > probable > possible > not likely related > unrelated) recorded for the event will be presented. If severity is missing, subjects will be included as missing (for severity). If drug relationship is missing, subjects will be included in related tables (e.g., considered related). Summary tables will be organized by SOC, then PT.

The following summaries will be presented for TEAEs:

- Overall Summary of TEAEs by Treatment
- Incidence of TEAEs by Treatment, System Organ Class and Preferred Term
- Incidence of Treatment Emergent Serious Adverse Events by Treatment, System Organ Class and Preferred Term

Subjects who prematurely discontinued due to TEAEs and subjects with serious TEAEs will be listed.

### **8.4.2 Laboratory Data**

Summary tables for laboratory parameters (including hematology, chemistry, and urinalysis) will be summarized for each treatment. Summaries for change from baseline for hematology, chemistry, and urinalysis parameters will include descriptive statistics (the number of non-missing values, mean, standard deviation, median, minimum and maximum) for values and change from baseline values for all continuous variables, and frequency counts and percentages for categorical variables, by treatment. Subjects with laboratory data outside the normal range will be listed with abnormal values flagged.

### **8.4.3 Vital Signs**

Summary tables for vital signs data will include descriptive statistics (the number of non-missing values, mean, standard deviation, median, minimum and maximum) for values and change from baseline values by treatment.

A listing of vital signs results will be provided for all subjects in the Safety Population.

### **8.4.4 Electrocardiogram (ECG)**

ECG parameters (RR interval, PR interval, QRS duration and QT interval) will be summarized by changes from baseline values by treatment using descriptive statistics. For each parameter, only subjects who had both baseline and a post-baseline assessment will be included in the summary.

A listing of ECG results will be provided for all subjects in the Safety Population.

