OTC	over-the-counter
PD	pharmacodynamic
PE	physical examination
Pgp	p-glycoprotein
PK	pharmacokinetic
QRS	The QRS complex is a name for the combination of three of the graphical deflections seen on a typical electrocardiogram
QT _c	The corrected QT interval is a measure of the time between the start of the Q wave and the end of the T wave in the heart's electrical cycle
RBC	red blood cell (count)
RR	respiration rate
SAE	serious adverse event
SD	standard deviation
SGLT1	sodium glucose cotransporter 1
SGLT2	sodium glucose cotransporter 2
SOP	standard operating procedure
t _{1/2}	apparent terminal elimination half-life
TBL	serum total bilirubin
TC	total cholesterol
TEAE	treatment emergent adverse events

TG	triglycerides
T _{last}	time of last measurable (positive) concentration
T _{max}	time of maximum observed plasma concentration
UGE	urinary glucose excretion
UGT1A9	UDP glucuronosyltransferase 1 family, polypeptide A9
ULN	upper limit of normal (value)
UTI	urinary tract infection
V _z /F	apparent volume of distribution
WBC	white blood cell (count)
WHO-DD	World Health Organization Drug Dictionary
WOCBP	women of childbearing potential
λ_z	Terminal elimination phase rate constant

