4.3 Exclusion Criteria

Subjects who meet any of the following criteria will be excluded from the study.

1. Subjects who are determined by the investigator or sub-investigator to be unsuitable for participating in the study based on medical conditions, including impairment of the central nervous system, circulatory system, respiratory system, blood/hematopoietic function system, gastrointestinal system, liver/kidney function, thyroid function, pituitary function and/or adrenal function.
2. Female subjects who are nursing or pregnant.
3. Subjects with a clinically significant history of allergy to drugs or latex.
4. Subjects with a history of alcohol or drug dependence in the last 12 months.
5. Subjects who had 400 mL of whole blood collected within four months or 200 mL of whole blood collected within one month of the screening test.
6. Subjects who had blood component collection within 14 days prior to the screening test.
7. Subjects who have used prescription or over-the-counter (OTC) drugs within 14 days prior to the first dose.

8. Subjects who have used vitamin preparations or supplements (including St. John's Wort and ginseng) within 14 days prior to the first dose.
9. Subjects who have undergone strenuous activity within 72 hours prior to Day 1 in each period.
10. Subjects who are unable (e.g., food intolerance) or unwilling to consume a high-fat breakfast within 25 minutes.
11. Subjects who have been treated with an investigational drug within 30 days or 7 half-lives of the investigational drug, whichever is longer, prior to the first dose of study drug in this trial.
12. Subjects who had previously received EGT0001474 or bexagliflozin, or any other SGLT2 inhibitors within 3 months from the screening.
13. Subjects whose screening electrocardiogram (ECG) demonstrates any one of the following: heart rate > 100 bpm, QRS > 120 msec, QTc > 470 msec (corrected by Bazett's formula), PR > 220 msec (a subject with PR > 220 msec will generally be excluded but exceptions may be allowed at the discretion of the investigator), or any rhythm that is not sinus rhythm, sinus bradycardia, or sinus arrhythmia.
14. Subjects whose sitting blood pressure is above 140/90 mmHg at screening.
15. Subjects who have a positive result of HBsAg antigen, HCV antibody, urinary drug or urinary cotinine test.
16. Subjects with known human immunodeficiency virus (HIV) disease.

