6.5 Electrocardiography and Continuous Telemetry Monitoring

6.5.1 12-Lead Electrocardiograms

A 12-lead electrocardiogram (ECG) will be conducted as listed in [Appendix 1](#) and whenever clinically indicated.

This procedure should be performed in the supine position after at least 10 min of rest. ECG parameters measured will be the RR interval, PR interval, QRS duration, and QT. Each ECG should also be assessed by the investigator for signs of ischemia, clinically significant hypertrophy, and clinically significant T-wave abnormalities.

It is the investigator or designee's responsibility to review the results of the ECG as they become available. For each abnormal ECG result, the investigator needs to ascertain if this is a clinically significant change from the screening ECG for that individual subject (this determination, however, does not necessarily need to be made the first time an abnormal result is observed. The investigator may repeat the ECG to verify the results of the original result). If the ECG result is determined to be a clinically significant and abnormal change from baseline for that subject, this is considered an AE.

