## **1. INTRODUCTION**

This Statistical Analysis Plan (SAP) outlines the statistical methods for the display, summary and analysis of data collected within the scope of Theracos Sub LLC protocol THR-1442-C-481 version 2 dated 20-May 2016. As with any SAP, the proposed methods and approaches to the data analysis should be deemed as flexible. The analysis of the data should allow changes in the plan to the extent that deviations from the original plan would provide a more reliable and valid analysis of the data. As such, the statistical analysis to a certain degree is iterative since much of the planning is based on assumptions that require verification. The purpose of this plan is to provide general guidelines from which the analysis will proceed. Nevertheless, deviations from these guidelines must be substantiated by a sound statistical rationale.

This SAP should be read in conjunction with the study protocol and the Case Report Forms (CRFs). This version of the SAP has been developed using the final version of the protocol mentioned above and the final version of the annotated CRFs dated 30-Jun-2016.

The SAP details the analysis of the data collected in the study and the presentation of the results of the analyses. The table, listing, and figure (TLF) shells are displayed in a companion document which provides information on the layout of the data displays.

All statistical analyses will be performed using SAS® version 9.3. Adverse events will be coded using the latest version of the Medical Dictionary for Regulatory Activities (MedDRA version 19.0 or newer).

This is a single center, phase 1, open-label,  $2 \times 2$  crossover study designed to assess the effects of a high-fat meal on the pharmacokinetics (PK) of orally administered bexagliflozin tablets. Approximately 18 eligible healthy subjects are planned to be randomized into two treatment groups such that an equal number ( $n = 9$ ) of subjects will receive a single oral dose of 20 mg of bexagliflozin with or without a meal on treatment day 1. Subjects randomized to receive bexagliflozin with a high-fat meal on day 1 will receive a second dose of bexagliflozin without a meal on treatment day 8 after an overnight fast. Subjects randomized to receive bexagliflozin without a meal on treatment day 1 after an overnight fast will receive a second dose of bexagliflozin with a high-fat meal on treatment day 8.

(See Protocol Sections 3.1 to 3.3 for details).

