#### **6. SPECIFICATION OF ENDPOINTS AND VARIABLES**

##### **6.1 Demographic and Baseline Characteristics**

Demographic variables consist of the following:

- Age in years (continuous) derived as the integer value of  $(\text{informed consent date} - \text{date of birth} + 1)/365.25$
- Sex
- Race
- Ethnicity

Baseline characteristics consist of the following:

- Weight (kg)
- Height (cm)
- Vital signs

- systolic blood pressure (SBP, mmHg)
- diastolic blood pressure (DBP, mmHg)
- oral temperature (°C)
- pulse (beats per minute)
- respiration rate
  
- Electrocardiogram (ECG) parameters
  - RR interval (msec)
  - PR interval (msec)
  - QRS duration (msec)
  - QT interval (msec)
  
- Medical and surgical history
- Clinical laboratory tests
- Prior and concomitant medication
- Physical examination

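### SAP 6.3.6 calls the QT interval corrected, but the row planned is uncorrected QT; the by-treatment ECG table would be clearer with QT defined as such and a QTc row added

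*SAP*

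**What the plan says.** Four places name the ECG variables, and all use plain QT. Protocol 6.5.1: "ECG parameters measured will be the RR interval, PR interval, QRS duration, and QT". SAP 6.1 lists QT in milliseconds among the baseline ECG parameters, next to RR, PR and QRS. SAP 6.3.6 names the same four. SAP 8.4.4 sets out the table: "ECG parameters (RR interval, PR interval, QRS duration and QT interval) will be summarized by changes from baseline values by treatment". None lists QTc.

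The explanation in SAP 6.3.6 conflicts with this. It reads "QT interval (the corrected QT interval is the measure of the time between the start of the Q wave", and continues to the end of the T wave. The protocol's list of abbreviations has almost the same sentence, but under QTc: "The corrected QT interval is a measure of the time between the start of the Q wave and the end of the T wave".

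The SAP gives no correction formula. Its glossary explains PR, QRS and RR interval but has no entry for QT or QTc, and its Appendix 1 on data handling has no QTc derivation. The only formula in either document is in Protocol 4.3, exclusion 13, for screening: "QTc > 470 msec (corrected by Bazett's formula". Protocol 9.6.3 asks for changes from baseline in intervals without naming them.

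**The concern.** Safety in the fasted and fed states is a secondary objective (SAP 2.2), ECG is a listed safety variable (SAP 6.3), and ECG changes are tabulated by treatment. A reader who takes the definition in SAP 6.3.6 at its word will believe that the QT row has been adjusted for heart rate, when the parameter lists show that it has not.

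The mislabelling matters because QT varies with heart rate. If heart rate changes from baseline by different amounts after fed and fasted dosing, the QT row will differ between treatments with no difference in repolarisation. A real difference could also be offset. Only the QT row is affected; PR, QRS and RR are not in question.

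**Working it through.** The documents state no figure on this point, so there is none to reproduce. The check has two parts.

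**Which variable is planned.** Protocol 6.5.1, SAP 6.1, the head term in SAP 6.3.6 and SAP 8.4.4 agree on RR, PR, QRS and QT. Against them stands one word in a parenthesis whose wording closely follows the protocol's QTc entry. Even that parenthesis describes a raw interval, Q wave to end of T wave. Uncorrected QT is the operative reading.

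**How far raw QT moves with heart rate.** The inputs are assumptions: resting rate 60 beats/min, rises of 0, 2, 5 and 10, and a true QTc that stays at 400 ms. The documents give no effect of the meal on heart rate. With RR = 60000/HR ms:

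- if Bazett holds, QT = QTc × (60/HR)^(1/2);
- if Fridericia holds, QT = QTc × (60/HR)^(1/3). This formula is in neither document and is used here only to show a range.

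| HR | QT, Fridericia | change | QT, Bazett | change |
|---|---|---|---|---|
| 60 | 400.0 | 0 | 400.0 | 0 |
| 62 | 395.7 | -4.3 | 393.5 | -6.5 |
| 65 | 389.5 | -10.5 | 384.3 | -15.7 |
| 70 | 380.0 | -20.0 | 370.3 | -29.7 |

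For a QTc of 380 to 420 ms, a rise of 5 beats/min gives -10.0 to -11.1 ms (Fridericia) or -14.9 to -16.5 ms (Bazett).

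Only a difference between treatments in heart-rate change distorts the comparison. If both rise by 5 beats/min, the spurious contrast is 0. If fed rises by 5 and fasted by 2, it is -10.5 - (-4.3) = -6.2 ms (Fridericia) or -15.7 - (-6.5) = -9.2 ms (Bazett).

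The opposite case, where raw QT hides a change, follows from QTcB = QT/(RR/1000)^(1/2). If QT stays at 400 ms while heart rate goes from 60 to 65, the QT change is 0, but QTcB goes from 400.0 to 400/(60/65)^(1/2) = 416.3 ms, a rise of 16.3 ms. If QT falls to 390 ms, the QT change is -10 ms and QTcB is 390/(60/65)^(1/2) = 405.9 ms, a rise of 5.9 ms. Size and sign can both depend on which variable is shown.

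**Bazett's own limit.** If QT follows the cube-root relation with QTcF constant at 400 ms, QTcB for the same recordings is 400.0, 402.2, 405.4 and 410.4 ms at 60, 62, 65 and 70 beats/min. On that assumption Bazett drifts upward by 0, 2.2, 5.4 and 10.4 ms. This shows that the formulas part when heart rate changes; it does not show which is right.

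**The case against.** The strongest case against is that this is an editorial slip. Every operative list says QT, no passage promises a QTc analysis, the table is consistent with Protocol 9.6.3, and deleting one word removes the contradiction. On that view, adding QTc is a reviewer's preference. The heart rates above are invented, and the post-dose ECG scheduled in both periods is at 4 h, about 4.5 h after the meal starts, where nothing in the documents points to a difference in heart rate.

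Much of this stands. A reader might infer that the plan leaves QT versus QTc open, or that the row cannot be derived because no formula is named. The documents do not support either inference: the lists agree on uncorrected QT, which needs no formula. Nor do they support saying that the fed-fasted ECG comparison will be biased.

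The limits on harm are also real. RR change is in the same table and pulse change is summarised (SAP 6.3.5 and 8.4.3), so a heart-rate difference would be visible. SAP 3.3 rules out formal testing. Investigators assess abnormal ECGs (Protocol 6.5.1). SAP 8.4.4 also says: "A listing of ECG results will be provided for all subjects in the Safety Population".

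Two parts of the objection do not carry. First, deleting the word leaves a table whose QT contrast still mixes in heart rate. Summary rows for QT and RR allow at best a rough mental adjustment: the correction is nonlinear and needs QT and RR from the same ECG. Deriving QTc later from listings, if they show both, would mean choosing the formula after seeing the data. Second, the shells might carry a clear label, but they were not available for this review. SAP 1 says "The table, listing, and figure (TLF) shells are displayed in a companion document" and gives their role as layout, while SAP 4 places analytic approaches in the protocol and the SAP.

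**Conclusion.** The point holds as a minor one. SAP 6.3.6 wrongly describes the QT interval as corrected, and the by-treatment table planned in SAP 8.4.4 gives change in raw QT only. Any fed-fasted difference in heart-rate change could therefore appear as, or mask, a QT difference, and the SAP's own definition would lead a reader to think this had been dealt with.

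The size is unknown and may be zero. The millisecond figures rest on an assumed resting rate, assumed rises and a constant QTc; they describe how the formulas behave and do not estimate what this trial will show. That the definition was copied from the protocol's QTc entry is an inference from the similar wording. The primary PK analysis is unaffected.

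**What to change.** In SAP 6.3.6, remove the word corrected from the explanation of QT. Define QTc as a separate variable, derived for each ECG from the recorded QT and RR (both in msec) as QT/(RR/1000)^(1/2). This is Bazett's formula, which exclusion 13 already uses, so screening and analysis values would be on the same scale. Fridericia, QT/(RR/1000)^(1/3), may be added as an option if named in advance.

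In SAP 6.1 add QTc to the baseline ECG parameters. In SAP 8.4.4 add QTc and its change from baseline by treatment, keep QT and RR, and label the rows so that corrected and uncorrected intervals are distinct. Match the table shells.

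The cost is one derived variable, one extra table row (two of each with Fridericia) and a few words of SAP text. It needs no new data or procedure. The drawback is Bazett's own dependence on heart rate, which is why RR should stay in the table beside it. The minimum change is to delete the word in SAP 6.3.6; that cures the mislabelling but leaves the comparison open to heart rate.
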